### 569 570 **3 Data Collection Visits: Baseline (week 0/Visit 1), post adoption phase (week** 571 **24/Visit 7a/b) and post maintenance phase (week 36/Visit 9) in all participants** 572 **(See appendix 8 for measures)**

573 At the data collection visits, the following procedures will take place at the Clinical  
574 Research Center at UIC or Chicago Park District location:

- 575 1. Secure informed consent (1st visit only).
- 576 2. Complete a brief demographic form.
- 577 3. Spirometry performed according to American Thoracic Society guidelines.  
578 Participants will be asked to wear nose clips and to take a deep breath in and  
579 blow their breath out as fast as they can into the spirometer. We will perform  
580 repeated measurements (3 to 8 times) to ensure accuracy of results.
- 581 4. Height and Weight
- 582 5. Incremental Shuttle Walk Test (ISWT) performed according to American  
583 Thoracic Society guidelines
- 584 6. Physical activity questionnaires

- 585 7. Asthma Safety Measures  
586 8. Asthma Control Questionnaire (ACQ)  
587 9. Asthma-related quality of life questionnaire (AQLQ)  
588 10. Adult Asthma Adherence Questionnaire (AAAQ)  
589 11. PROMIS measures (Global Health, social roles satisfaction, mood, sleep)  
590 12. Active Where Questionnaire  
591 13. Self-efficacy for walking scale  
592 14. Social support for exercise survey  
593 15. Outcome expectation scale for exercise  
594 16. Sleep Apnea Scale of the Sleep Disorders Questionnaire  
595 17. Pittsburgh Sleep Quality Instrument  
596 18. Neighborhood safety and social cohesion questionnaire  
597 19. Study randomization (1st visit only)  
598 20. Schedule asthma and physical activity (PA) education session with participant  
599 (1st visit only)  
600

601 Key research personnel will obtain consent in a private room in the Clinical  
602 Research Center. After consent is obtained, the other study procedures will be  
603 completed.  
604

605 This visit will last approximately 2 hours and upon completion the participant will  
606 receive \$35 cash or gift card. Patients will be offered light snacks/refreshments  
607 at this visit and given a visit summary sheet with their blood pressure, heart rate,  
608 weight, height, oxygen level, date of next study visit and a copy of spirometry  
609 results if desired.  
610

611 Participants will then be provided the following equipment at these data collection  
612 visits:

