613 Actigraph accelerometer: This will be given to participants to assess their baseline  
614 and post-intervention daily number of steps. Participants will be verbally instructed  
615 to wear it attached to their wrist at all times while awake. The Actigraph  
616 accelerometer (Figure 3) is a research accelerometer (1.8 inches at its largest  
617 dimension, weight 19 grams). This will be returned within 2 weeks of the data  
618 collection visit. The accelerometers can be returned either in person at the asthma  
619 and PA session, in a postage paid envelope or the participant and the research  
620 assistant will find a mutually agreeable place to pick up the accelerometer from the  
621 participant. The participant will not incur any charges if the accelerometer is lost or  
622 stolen. The data from the accelerometers will be downloaded to Actigraph software  
623 (ActiLife 6.13.3) when the accelerometers are returned. Only study ID will be used

624 in the actigraph software. No identifiable information will be maintained in the  
625 Actigraph software.

626  
627 Participants are typically asked to wear the accelerometer for 7 days (does not  
628 have to be consecutive). However, valid baseline measurement of activity can be  
629 obtained with an average of 10 hours per day for 4 days. This is the minimum  
630 amount of accelerometer data required to continue participation in the intervention.  
631 If the participant does not wear the accelerometer for sufficient time to provide valid  
632 baseline measure (ie. an average of 10 hours per day for 4 days), they will be  
633 offered a second opportunity to wear the accelerometer. If the participant declines  
634 or is unable to wear the accelerometer again within 3 weeks of returning the  
635 accelerometer, then the participant will be withdrawn from the study.

636  
637 **Enhanced Usual Care Group (home-based walking program):** The comparison  
638 group will be instructed to achieve a static goal of 10,000 steps per day. The US  
639 Surgeon General recommends accumulating 30 minutes of activity most days of the  
640 week. Assuming that an individual gets 6,000 steps from their other daily activities, 30  
641 minutes of walking can help one achieve a goal of approximately 10,000 steps per day.

642  
643 Participants will be given a Fitbit Charge HR® which will measure their daily steps (see  

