644 more detail below under visit 2). In order to attention-match for interactions with study  
645 staff, participants will attend an asthma education and physical activity training session.  
646 Newsletters with walking tips for AA women and asthma education topics will be sent  
647 twice during the intervention phases to participants in this group. Participants will come  
648 to the Clinical Research Center for data collection at weeks 24 (Visit 7b) and 36 (Visit 9)  
649 described in more detail below.

650  
651 **Asthma and physical activity (PA) education session for all participants (1-6**  
652 **weeks after baseline data collection visit)**

653 The asthma and PA education session will take place at UI Health/UIC or a Chicago  
654 Park District (CPD) location that is in close approximation to where the participants live.  
655 The exact CPD location will be determined with the help of the Chicago Park District  
656 liaison and will take into account safety of the participants and the location of where  
657 participants live. The Chicago Park District will only provide space for these visits and  
658 no Chicago Park District staff are involved in the research as recruiters or to collect  
659 data. Two separate asthma/PA education sessions will take place, one for enhanced  
660 usual care group and one for those randomized into the intervention group.

661  
662 At the asthma/PA education session the following procedures will occur:

663 1. Collection of accelerometers for those that have not already returned it.

- 664 2. Attend a 2 hour group session at the Chicago Park District or at UI  
665 Health/UIC. At the group session, participants will receive didactic asthma  
666 education and information on how to engage in physical activity with their  
667 asthma.  
668 3. Participants will be asked to complete a session evaluation form. (Appendix 9)  
669 4. Participants will be given \$5 cash to assist with travel expenses incurred for  
670 the visit.

671  
672 Key research personnel will send a reminder text, call and/or email (based on patient  
673 preference) up to 3 times the prior week to the group session stating “Asthma and  
674 physical activity session will meet at X time and X place.”  
675

676 An asthma educator, a research assistant(s) and/or [name] will attend the  
677 education session. Each education session will last approximately 2 hours. Patients will  
678 receive light snacks/refreshments at each session.  
679

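### Aim 3 randomises before baseline accelerometer wear can be checked, then withdraws randomised women who fail the wear minimum, with no stated follow-up

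*Combined protocol and SAP*

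**What the plan says.** Section 6.0, Aim 3, lists the procedures of the three data collection visits. Item 19 is "Study randomization (1 st visit only"). After the list comes the equipment: "Participants will then be provided the following equipment at these data collection" visits. The accelerometer is therefore issued after randomisation. On its return the text says "This will be returned within 2 weeks of the data" collection visit, and the data are downloaded once it is back.

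The minimum for a valid baseline is an average of 10 hours a day over 4 days. The plan first describes this as the "amount of accelerometer data required to continue participation in the intervention". A woman who falls short is offered a second wear. If she declines "or is unable to wear the accelerometer again within 3 weeks of returning the" device, the consequence is "accelerometer, then the participant will be withdrawn from the study". The rule is not limited to one arm.

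Section 10.0 (progress and safety monitoring) says that a woman who cannot give acceptable accelerometer data, or who is withdrawn, is sent a final letter. It provides for reviewing summaries of withdrawals, but mentions no further outcome visit.

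On timing, one permitted route begins "The accelerometers can be returned either in person at the asthma" and PA session. That session is headed "education session for all participants (1-6" weeks after baseline). It is run separately for each arm, and the Fitbit is issued there.

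**The concern.** A rule applied after allocation decides who stays in the trial. Some women may know their arm when they decline a second wear, because the separate education sessions fall in the same weeks. If withdrawal then differs by arm and is related to outcome, the comparison of arms is no longer protected by randomisation. Aim 3 is meant to estimate efficacy so that a later trial can be powered, and to assess feasibility, which retention informs.

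The rule also gives up usable data. Spirometry, the shuttle walk test, the ACQ and the AQLQ are measured at Visit 1 (items 3, 5, 8 and 9) and do not depend on accelerometer wear. A woman without valid baseline steps could still contribute to all four at weeks 24 and 36.

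A second issue is the quality of a repeated baseline. A re-wear that follows arm-specific training and issue of the Fitbit no longer measures activity before the intervention.

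**Working it through.** There is no plan figure to reproduce: Section 11.0 states that no sample size calculation was made for Aim 3. The check is a reading of the sequence, followed by arithmetic for scale.

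**Sequence.** Randomisation is at week 0. Return is due by week 2, and re-wear is allowed for 3 weeks after return, so with on-time return the decision can fall as late as 2 + 3 = week 5. Education sessions run in weeks 1-6.

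**Re-wear after training.** A device mailed back at week 2, a session at week 3 and re-wear in weeks 4-5 meets every stated limit. Contamination depends on whether re-wear follows the session, not on how the device was returned. Item 1 of the session procedures also plans collection there from women who have not yet returned the device. At a week 6 session this allows re-wear up to 6 + 3 = week 9.

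**Is a withdrawn woman followed?** Three places come closest.
- The headings for data collection (Aim 3 visits and post-maintenance) refer to all participants, but do not say that this includes someone already withdrawn.
- The make-up data visit covers an intervention woman who cannot attend the last adoption session.
- The investigator's case-by-case discretion concerns missed education sessions.

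None of these covers wear failure. Sections 9.0 and 11.0 give no analysis set, missing-data rule or between-arm analysis for Aim 3.

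**Scale.** Inputs: 80 women (Section 11.0, an upper limit). Assumed: 40 per arm, equal loss by arm, and failure without re-wear in 5%, 15% or 25%.
- Women affected: 80 × 0.05 = 4; 80 × 0.15 = 12; 80 × 0.25 = 20.
- Follow-up assessments lost, at most two each: 8, 24 or 40.
- 95% half-width in SD units, 1.96 × √(2/n per arm): n = 40 gives 0.438; n = 38, 0.450; n = 34, 0.475; n = 30, 0.506. The increases are about 3%, 8% and 15%, before other dropout.

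**Bias.** Let p be the share withdrawn in an arm, and d the mean outcome of women kept minus that of women withdrawn. The mean of those kept exceeds the full-arm mean by p × d, so the bias in the difference is p1·d1 − p0·d0. It is zero only if the two products are equal.
- 15% v 5%, common gap 0.5 SD: 0.15 × 0.5 − 0.05 × 0.5 = 0.05 SD.
- 15% v 5%, common gap 1.0 SD: 0.15 − 0.05 = 0.10 SD.
- Equal 15% withdrawal, gaps of 1.0 and 0.5 SD: 0.15 × (1.0 − 0.5) = 0.075 SD. Equal rates alone do not remove bias.

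The 0.05-0.10 SD range is 11-23% of the 0.438 half-width. The sign can go either way.

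**Retention.** With 12 wear failures and 60 completers (both hypothetical), retention is 60/80 = 75% or 60/68 = 88%, depending on the denominator.

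**The case against.** The best defence is that the rule has a purpose: individual step goals are set from baseline accelerometer data. That holds for the intervention arm only, because the goals are given in its group sessions. Enhanced usual care has a static goal of 10,000 steps a day, which needs no baseline. Even in the intervention arm, the reason concerns one treatment component and does not explain ending outcome collection.

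A reader might infer that the plan contradicts itself, tying the minimum to the *intervention* in one sentence and to the *study* in another. The documents do not support that firmly. Section 6.0 speaks of intervention phases when describing newsletters to usual care women, and Section 12.1 uses the word for all participants in Aims 2 and 3. Section 10.0 points women with unacceptable accelerometer data to the letter for withdrawn participants, which fits treating wear failure as a route to withdrawal. The wording is ambiguous and should be clarified.

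It is also fair to say that the rates are all assumed, that this is a feasibility pilot, and that with no between-arm analysis specified the rule removes nobody from a defined analysis set. The plan does not say that collected data are discarded, nor that retention will be computed on the smaller denominator. These points limit the size of the concern. They do not supply the missing follow-up.

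**Conclusion.** The point stands as a stated rule for exclusion after randomisation, in both arms, without provision for follow-up. It is worth fixing because the remedy is cheap, but the likely harm is modest.

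A reader might infer that the efficacy estimate is bound to be biased. The documents do not support this: bias needs unequal products of withdrawal share and outcome gap, and nothing shows what either will be. In the illustrated case (5% v 15%, common gap) it is small beside the pilot's imprecision. The precision loss, to 0.45-0.51 SD, rests on the assumed 5-25% failure and 40 per arm.

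The order of events is explicit in the text. The absence of follow-up is inferred from silence; Figure 2 and the Appendix 7 procedures table were not available for this check.

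**What to change.** Amend the wear rule in Section 6.0 and the matching text in Section 10.0, and clarify whether the minimum concerns the intervention or the study. Suggested wording: *A randomised participant without valid baseline wear remains in the study for week 24 and week 36 data collection and is analysed in her allocated arm, with baseline steps treated as missing.* Carry this into the Aim 3 text of Sections 9.0 and 11.0.

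Report retention over all randomised women, with wear failures shown separately by arm. Flag any baseline re-worn after the education session, and analyse change in steps with and without those values. The sponsor should state how the step-goal component is handled for a woman without a valid baseline; this review proposes no rule for that.

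The cost is text edits plus up to two visits per affected woman. At $35 per data collection visit, that is 2 × $35 = $70 each: 4 × $70 = $280 to 20 × $70 = $1,400 in participant payments at the assumed rates. Staff time at existing visits is extra and is not given. Some of these women may not attend.

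An alternative is to randomise only after valid wear is confirmed. That needs a separate randomisation contact and more recruitment to reach 80. Scheduling is also tight: re-wear to week 5 leaves about 1 week before the 6-week session limit.

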680 For missed sessions, make-up sessions will be offered (in-person or by video).  
681 Continuation in the program will be decided by the PI on a case by case basis.  
682 Participants will be strongly encouraged to make up missed sessions prior to the next  
683 scheduled group session (intervention group) or data collection visit (enhanced usual  
684 care group).  
685

686 Participants will be given the following equipment at the asthma/PA education session:  
687 1) Fitbit® physical activity monitor: Participants will be verbally instructed to wear it on  
688 their wrist at all times while awake. The Fitbit (Figure 4) is a commercially-available  
689 physical activity monitor (0.83 inches wide, weight 0.8 ounces). The wristbands are  
690 adjustable and data from our focus groups revealed that participants would prefer a  
691 wrist-based than a waist-based physical activity monitor. Participants will be asked to  
692 download the fitbit app to their smartphone or tablet and asked to create an account.  
693 Participants will be referred to the Fitbit website for troubleshooting. This will allow for  
694 physical activity data transmission to the Fitbit study database which will not contain any  
695 identifiable information. If a participant is unable to or does not want to download the  
696 fitbit app then they will write their daily steps into a journal which they will bring to each  
697 study visit. Participants will not be responsible for the cost of the Fitbit if it is lost or  
698 stolen.  
699

700 Daily physical activity, heart rate and status of the Fitbit (e.g., battery) will be monitored  
701 in real time using a Fitbit study database. Only physical activity data (i.e., step counts,  
702 time worn using heart rate, minutes active, distance walked) of the participant will be  
703 kept in the Fitbit study database. This is necessary for recording of detailed physical

704 activity data as the pedometers have limited data storage capacity. Only study ID will be  
705 used in the Fitbit study database. No identifiable information will be maintained in the  
706 Fitbit database.

707  
708 **Group sessions (Intervention group only):** Women randomized into the intervention  
709 group will also attend group sessions in 2 phases: Adoption and Maintenance (See  
710 Figure 2).

711  
712 **Adoption phase (5 sessions every 4 weeks)**

713 The group session will take place at UI Health/UIC or a Chicago Park District (CPD)  

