749 repeated measurements (3 to 8 times) to ensure accuracy of results.
- 750 2. Weight
- 751 3. Incremental Shuttle Walk Test (ISWT) performed according to American  
752 Thoracic Society guidelines
- 753 4. Accelerometer distribution
- 754 5. Summative evaluation (visit 7 only; Appendix 10)

755

756 If a participant is not able to attend this session, we will contact the patient to scheduled  
757 an in person data collection visit at UI Health/UIC where the above procedures (#1-3)  
758 will be completed.

759

760 During or after Visit 7a is complete, participants will complete REDCap paper surveys (  
761 in person) or will be sent a link (email or text) to complete the following REDCap  
762 surveys electronically:

- 763 1. Physical activity questionnaires
- 764 2. Asthma Safety Measures
- 765 3. Asthma Control Questionnaire (ACQ)
- 766 4. Asthma-related quality of life questionnaire (AQLQ)
- 767 5. Adult Asthma Adherence Questionnaire (AAAQ)
- 768 6. PROMIS measures (Global Health, social roles satisfaction, mood, sleep)
- 769 7. Active Where Questionnaire
- 770 8. Self-efficacy for walking scale
- 771 9. Social support for exercise survey
- 772 10. Outcome expectation scale for exercise
- 773 11. Sleep Apnea Scale of the Sleep Disorders Questionnaire
- 774 12. Pittsburgh Sleep Quality Instrument

775 Key research personnel will send a reminder text, call and/or email (based on patient  
776 preference) up to 3 times the prior week to the group session stating “ACTION Asthma  
777 group will meet at X time and X place.”

778

779 Reminder messages will also be sent via phone, text or email (based on participant  
780 preference) up to 3 times per week to help them attain their weekly step goal (See  
781 Appendix 11 for sample text messaging).

782

783 An interventionist and/or [name] will attend the group sessions. Each group will  
784 last approximately 2 hours and may be audio-recorded to assess for intervention fidelity.  
785 If a participant declines audio-recording the session, then the session will not be  
786 recorded. The PI or co-investigator may then observe a group session intermittently to  
787 assess for intervention fidelity. If the session is recorded, the PI will review portions of  
788 the session. The sessions will be deleted once the pilot is complete. These audio  
789 recordings will not be transcribed. Patients will receive light snacks/refreshments at  
790 each session.

791

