837 **Visit 7) Booster session will only be for intervention group.**

838

839 At visit 8 booster session the following procedures will occur:

- 840 1. Attend a 2 hour group session at the Chicago Park District or at UI  
841 Health/UIC. At the group session, participants will review successes attained  
842 and barriers, lapses, and relapses encountered.
- 843 2. Participants will be asked to complete a session evaluation form. (Appendix 9).
- 844 3. Participants will be given \$5 cash to assist with travel expenses incurred for  
845 the group visit.

846

847 An interventionist and/or [name] will attend the group session. The group will last  
848 approximately 2 hours and may be digitally recorded to assess for intervention fidelity. If  
849 a participant declines audio-recording the session, then the session will not be  
850 recorded. The PI or co-investigator may then observe a group session intermittently to  
851 assess for intervention fidelity. If the session is recorded, the PI will review portions of  
852 the session. The session will be deleted once the pilot is complete. These audio  
853 recordings will not be transcribed. Patients will receive light snacks/refreshments at the  
854 session.

855

856 **Post-maintenance data collection (all participants)**

857 The following procedures will take place at the Chicago Park District (intervention  
858 group) or Clinical Research Center at UIC (enhanced usual care):

- 859 1. Spirometry performed according to American Thoracic Society guidelines.  
860 Participants will be asked to wear nose clips and to take a deep breath in and  
861 blow their breath out as fast as they can into the spirometer. We will perform  
862 repeated measurements (3 to 8 times) to ensure accuracy of results.

- 863 2. Weight  
864 3. Incremental Shuttle Walk Test (ISWT) performed according to American  
865 Thoracic Society guidelines  
866 4. Distribution of accelerometer  
867  
868

869 The following questionnaires will be completed by REDCap survey:

- 870 1. Physical activity questionnaires  
871 2. Asthma Safety Measures  
872 3. Asthma Control Questionnaire (ACQ)  
873 4. Asthma-related quality of life questionnaire (AQLQ)  
874 5. Adult Asthma Adherence Questionnaire (AAAQ)  
875 6. PROMIS measures (Global Health, social roles satisfaction, mood, sleep)  
876 7. Active Where Questionnaire  
877 8. Self-efficacy for walking scale  
878 9. Social support for exercise survey  

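### The education session described as attention-matching the control arm goes to both arms, so all of the intervention arm's extra contact is unmatched and an effect cannot be credited to content over contact

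*Combined protocol and SAP*

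**What the plan says.** In Section 6.0, Aim 3, the paragraph on the Enhanced Usual Care Group gives the reason for the control arm's session: "In order to attention-match for interactions with study" "staff, participants will attend an asthma education and physical activity training session". Beyond this, controls are sent two newsletters during the intervention phases and are given a fixed target of 10,000 steps a day.

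The next heading in the same section reads "Asthma and physical activity (PA) education session for all participants (1-6" (weeks after baseline). It therefore covers both arms, and the text adds that the arms are taught apart: "data. Two separate asthma/PA education sessions will take place, one for enhanced" usual care and one for the intervention group. On length: "education session. Each education session will last approximately 2 hours. Patients will" also be given refreshments.

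The intervention arm then has further contact that controls do not:

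- Group sessions headed as being for the intervention group only, beginning with "Adoption phase (5 sessions every 4 weeks"). Each lasts 2 hours and includes sharing of experiences among the women.
- Step-goal reminders by phone, text or email, sent according to participant "preference) up to 3 times per week to help them attain their weekly step goal (See" the sample-message appendix). In the maintenance phase these fall to at most one a week.
- A 2-hour group session at Visit 8: "Booster session will only be for intervention group".
- A personal step goal, capped at 3,000 steps over the woman's own baseline.

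Section 3.0 gives the purpose of Aim 3 as assessing acceptability and feasibility and estimating efficacy so that a later trial can be powered. Section 11.0 describes no Aim 3 analysis that would separate contact from content.

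**The concern.** A component that both arms receive cannot offset contact that only one arm receives. The protocol nevertheless gives attention matching as the reason for the control session, and it describes no other attention control.

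What is at stake is the meaning of the efficacy estimate. Many Aim 3 outcomes are self-reported: asthma control, asthma quality of life, the PROMIS measures, walking self-efficacy and social support for exercise. No blinding of participants is described, and the arms differ visibly. If the control is reported as attention-matched, readers will take a difference on these scales as the effect of the walking and asthma content. It could equally come from additional hours with an interventionist and a peer group. The next trial would then be designed on that reading.

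**Working it through.** The documents state no total contact hours and no Aim 3 sample-size calculation, so there is no stated figure to reproduce. The check is a sum of scheduled hours by arm.

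**Inputs (all Section 6.0, Aim 3)**

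- Education session: about 2 h, both arms.
- Adoption sessions: 5 of 2 h each, intervention arm only.
- Booster session: 2 h, intervention arm only.
- Data-collection visits: baseline, week 24 and week 36, both arms, about 2 h each.

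**Programme contact, excluding data-collection visits**

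- Intervention: 2 + 5×2 + 2 = 14 h.
- Control: 2 h.
- Ratio 14/2 = 7; difference 14 − 2 = 12 h.
- Up to the week-24 assessment (no booster yet): 2 + 5×2 = 12 h against 2 h, a ratio of 6.

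The shared 2 h cancels in the difference. The 12 h that remain are exactly the five adoption sessions and the booster (5×2 + 2), and the education session offsets none of them.

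**Programme contact plus data-collection visits**

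Control: 2 + 3×2 = 8 h.

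For the intervention arm the total depends on whether later measurements fit inside a group session or add to it. The week-24 measurements are taken at the last adoption session, and the surveys can be completed by electronic link. The post-maintenance measurements are described alongside the booster. Neither text says whether they lengthen the session.

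| Week-24 and week-36 measurements, intervention arm | Intervention | Control | Ratio | Difference |
|---|---|---|---|---|
| Both inside group sessions | 14 + 2 = 16 h | 8 h | 2.0 | 8 h |
| One inside, one adding 2 h | 14 + 4 = 18 h | 8 h | 2.25 | 10 h |
| Both adding 2 h | 14 + 6 = 20 h | 8 h | 2.5 | 12 h |

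**Messages**

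The length of the reminder period is not stated, so I assume 16 weeks (four 4-week gaps between five sessions) to 24 weeks (baseline to the week-24 visit).

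- Adoption: at most 3×16 = 48 to 3×24 = 72 reminders.
- Maintenance: 12 weeks at no more than one a week, so at most 12.

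These are ceilings, not expected counts. The comparison with two newsletters is not like for like, because controls also get appointment reminders and accelerometer-return reminders. That the maintenance messages go only to the intervention arm is implied, since participants are said to keep receiving them, but it is not stated outright.

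**The case against.** Much of the case on the other side is sound, and it limits what can be claimed.

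**The 7:1 ratio overstates total staff contact.** The protocol speaks of interactions with study staff, and measurement visits are such interactions. This stands. The 14 h against 2 h figure holds only for programme sessions, and the ratio over all scheduled contact is 2.0 to 2.5.

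**The session does some matching.** A reader might infer that it matches nothing. The documents do not support that: both arms get the same length of asthma and physical activity education, and without it controls would have no programme session at all. Matching is partial and covers that component only.

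**Group contact is part of the intervention.** A reader might infer that the trial comparison is invalid or confounded. It is not. Group discussion is a designed element, the comparator is named enhanced usual care, and randomisation supports a comparison of one package with the other. No section commits the investigators to crediting an effect to content over contact, so the harm depends on how the control is later described.

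**Contact and content are not the only differences.** The arms also have different step goals. This stands, and any definition of the package must include them.

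**Objective step counts do not escape the problem.** A reader might infer that ActiGraph steps are protected from attention effects. They are less open to self-report bias, but the reminders are meant to help women reach a step goal, so contact can act on walking itself.

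**This is a pilot.** No analysis, sample size or randomisation element depends on the phrase. That limits the seriousness of the point but does not remove it, because the pilot's estimate is meant to inform the next trial.

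**Conclusion.** The point holds as a mismatch between a stated property and the design. Attention matching is claimed, but the session said to provide it goes to both arms and leaves 12 scheduled programme hours in the intervention arm unmatched. Even with data-collection visits counted, the excess is 8 to 12 h. No reasonable count makes the arms equal.

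The consequence is confined to interpretation. Aim 3 can estimate the effect of the whole package against enhanced usual care. It cannot say how much of a difference is due to content, staff and peer contact, messages or step goals. This should be corrected, but it does not undermine the trial.

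The hours are as scheduled and assume full attendance and data-collection visits of about 2 h. The pilot procedures table (Appendix 7) and the Aim 3 design figure could not be seen.

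**What to change.** 1. In Section 6.0, Enhanced Usual Care Group, delete the attention-matching wording. A neutral replacement would be: *both arms attend a 2-hour education session; contact beyond that session is not matched*.
2. In Sections 3.0 and 11.0, define the Aim 3 contrast as the whole ACTION package (content, group contact, messaging and individualised step goals) against enhanced usual care.
3. State that the efficacy estimate carried to the next trial will not be attributed to content over staff and peer contact.
4. Report attended session hours by arm, separately from data-collection time. Section 10.0 already provides for attendance to be reviewed weekly and summarised in reports. Add message counts only if sending records exist, since the documents do not say that messages are logged.
5. Describe ActiGraph steps as less open to self-report bias, not as free of attention effects.
6. State which arm receives the maintenance-phase messages.

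The cost is a change of wording and one table, largely from data already reviewed. It needs no new visits, participants or procedures. The downside is a more modest claim.
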